cohorts will be selected based on preliminary safety and available PK and PD data. The doses selected for Part C will not exceed the MTD (or MAAD if no MTD is determined) in Part B, but may incorporate assessment of other data including toxicities and PK, PD data from Parts A and B, as well as feasibility and bioavailability (BA) of SC administration from Part A1.

Sentinel Participant:

During the dose escalation phase in Part A, Part A1, and Part B, a staggered dosing (sentinel participant) approach will be used. In Part A and Part A1, the first participant to be dosed at Cycle 1 Day 1 of the first dose level will be observed for 5 days before additional participants (ie, Participant 2 onward in that cohort) receive study treatments in the same dose level. In Part B, the first participant to be dosed at Cycle 1 Day 1 of each dose level will be observed for 5 days before additional participants (ie, Participant 2 onward in that cohort) receive study treatments in the same dose level.

[figure not shown]
Initially, 3 participants will be enrolled at the start of each cohort, in accordance with the sentinel participant approach cited above. However, to allow for any unforeseen discontinuations (such as disease progression) before the 4-week DLT period (28 days) is completed, an extra participant may be enrolled in each dose escalation cohort. Therefore, there may be a total of 4 participants (3 + 1) at the start of each cohort, provided that the fourth participant is able to start dosing within approximately 1 week of the third participant in the same dose escalation cohort. Additional information on DLTs can be found in Section 7.1.1.

5.1.3.1 BMS-986258 Monotherapy Dose Escalation (Part A) (Including NSCLC PD Cohorts) and Subcutaneous Dose (Part A1)

In dose escalation, each participant will be administered IV doses of BMS-986258 in planned dose levels of 8, 24, 72, 200, 480, 800, 1200, 1600, and 2400 mg Q4W twice per cycle, for up to 12 cycles (96 weeks) of study therapy.

monotherapy dose cohorts may be in the escalation phase based upon the BLRM analysis and clinical evaluation of all available safety and PK/PD data. Participants enrolled in the NSCLC PD cohorts will receive a dose level that has already been cleared for safety within the corresponding dose escalation cohort.

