7.1 Treatments Administered

The selection and timing of dose (Table 7.1-1) for each participant is as follows:

Table 7.1-1: Selection and Timing of Dose

Study Treatment	Unit Dose Strength(s)/Dosage Level(s)	Dosage Formulation Frequency of Administration	Route of Administration	Infusion Time
BMS-986258	8, 24, and 72 mg ^{a,b}	Q4W	IV	See note ^b
	200, 480, and 800 mg ^b	Q4W	IV	
	1200 mg ^b	Q4W	IV	
	1600 mg ^b	Q4W	IV	
	2400 mg ^b	Q4W	IV	
Nivolumab	480 mg ^b	Q4W	IV	30 minutes
BMS-986258 + ENHANZE® Drug Product (rHuPH20)	1200 mg	Once	SC	

Abbreviations: IV, intravenously; Q4, every 4 weeks; rHuPH20, recombinant human hyaluronidase PH20; SC, subcutaneous.

Protocol Amendment No.: 07

^a ENHANZE[®] (rHuPH20) is referred as rHuPH20 in the protocol

b For study drugs preparation and infusion times, please refer to the Pharmacy Manual.

Intravenous (IV) BMS-986258:

Participants in Part A, Part A1 (after the first dose), and NSCLC PD cohorts will receive IV BMS-986258 as monotherapy at doses ranging from 8 mg to 2400 mg. After the first dose, participants in cohort A1 will be offered the option to receive subsequent IV BMS-986258 in combination with nivolumab (480 mg) at the highest dose of BMS-986258 that has been shown to be safe and tolerable in the dose escalation (Part B). Treatment will be given Q4W twice per cycle, for up to twelve 8-week cycles (96 weeks).

There will be no dose escalations or reductions of BMS-986258 allowed. For Q4W dosing cycles, participants may be dosed within a ± 3 -day window.

BMS-986258 will be administered through an IV line. For details in study drug preparation and administration, refer to Pharmacy Manual.

Subcutaneous (SC) BMS-986258:

Participants in Part A1 will receive BMS-986258 plus rHuPH20 as an SC injection. BMS-986258 + rHuPH20 will be administered subcutaneously via a syringe pump (refer to Pharmacy Manual) on Cycle 1 Day1.

Nivolumab:

Participants in Part A1 who have received combination therapy and participants in Part B, Part B NSCLC PD, and Part C cohorts should receive nivolumab at a dose of 480 mg as a 30-minute infusion on Day 1 of each treatment cycle every 4 weeks until progression, unacceptable toxicity, withdrawal of consent, completion of of treatment, or the study ends, whichever occurs first. Participants should begin study treatment within 3 calendar days of treatment assignment.

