There will be no dose escalations or reductions of nivolumab allowed. For Q4W dosing cycles, participants may be dosed within a ± 3 -day window. Premedications are not recommended for the first dose of nivolumab.

Participants should be carefully monitored for infusion reactions during nivolumab administration. If an acute infusion reaction is noted, participants should be managed according to Section 7.4.3.

Doses of nivolumab may be interrupted, delayed, or discontinued depending on how well the participant tolerates the treatment. Dosing visits are not skipped, only delayed. Nivolumab injection will be administered as an IV infusion over approximately 30 minutes.

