7.1.1 Dose-Limiting Toxicities

For the purpose of guiding decisions regarding dose escalation in Parts A and B, DLTs will be defined based on the incidence, intensity, and duration of AEs for which no clear alternative cause is identified. The DLT period will start on the first day of Cycle 1 and end at Day 28 (therefore, 4 weeks) in Parts A and B. The severity of AEs will be graded according to NCI CTCAE v4.03.

[figure not shown]
Protocol Amendment No.: 07

For the purpose of participant management, DLTs that occur at any time, whether during dose escalation (Part A or B), SC dose(s) (Part A1), or cohort expansion (Part C), will result in study drug being held pending evaluation of the event being related to study drug, in accordance with Section 7.4.

A participant is considered DLT evaluable if receiving 1 dose of BMS-986258 in Part A or 1 dose of BMS-986258 and nivolumab 480 mg in Part B and completing the DLT observation period. Participants who withdraw from the study during the 4-week DLT evaluation period for reasons other than a DLT may be replaced with a new participant at the same dose level. The incidence of DLT(s) during the 4-week DLT evaluation period will be used in dose escalation decisions and to define the MTD/RP2D in monotherapy and in combination with nivolumab. AEs occurring after the 4-week DLT period will be considered for the purposes of defining the RP2D upon agreement between the Sponsor and Investigators. Participants experiencing a DLT will not be retreated with study drug and will enter the safety follow-up period of the study.

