7.4.1 Dose Delays Due to Toxicity

Participants who experience the following must have all study drug(s) withheld:

• Potential DLTs, until DLT relatedness is defined.

- AE, laboratory abnormality, or concurrent illness that, in the judgment of the Investigator, warrants delaying study drug administration.
- Confirmed SARS-CoV-2 infection.

Criteria for participants who are required to permanently discontinue both study drugs are listed in Section 8.1. Participants not meeting guidelines for permanent discontinuation will be permitted to resume therapy based on the criteria specified below in Section 7.4.2. Participants eligible to resume study therapy will resume study therapy at the nominal treatment visit following their last received study medication dose.

The end of cycle tumor assessments, such as computed tomography (CT), magnetic resonance imaging (MRI), or positron emission tomography (PET), will continue on a Q8W schedule relative to the participant's first dose, regardless of any treatment delay incurred.

Protocol Amendment No.: 07

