10.1.1 Dose Escalation

During the dose escalation phase, an adaptive dose escalation scheme (BLRM for monotherapy and BLRM-copula for combination therapy) employing the EWOC principle will be used. The method is fully adaptive, makes use of all the information available at the time of each dose assignment, not just data from the current dose level, and directly addresses the ethical need to control the probability of overdosing.

The operating characteristics of BLRM for monotherapy escalation and BLRM-copula for combination therapy escalation were studied in various scenarios through simulations in .

The maximum number of participants treated will be for dose escalation Part A (BMS-986258 monotherapy) and for Part B (BMS-986258 in combination with nivolumab).

Approximately participants will be treated at the starting dose levels of BMS-986258 or BMS-986258 in combination with nivolumab. While the BLRM/BLRM-copula will use DLT information from the DLT period only, clinical assessment will take into consideration the totality of available data including PK/PD from all treated participants encompassing monotherapy and combination therapy, in assigning a dose level for the next cohort of participants. At least DLT-evaluable participants will be treated at the MTD. At most DLT-evaluable participants will be treated at each dose level. Additional participants may be treated at or any dose level below the estimated MTD for further evaluation of safety, PK, or PD parameters as required for a total of up to across doses for monotherapy and for combination therapy.

The final recommended MTD/RP2D will be based on the recommendation from the BLRM/BLRM-copula and overall clinical assessment of all available safety, PK, PD and efficacy data. Lower doses of BMS-986258 may be tested if none of the planned doses are found to be tolerable as monotherapy or in combination with nivolumab. Such decisions will be made after discussion and agreement between the Investigators and the BMS Medical Monitor.

Sample size calculations for the SC study (Part A1) are based on width of the confidence interval for the geometric mean ratio (GMR) of exposure measures for SC and IV dosing. For each dose to be tested in Part A1, the PK parameters are assumed to be distributed log-normally,

To account for potential missing data, approximately subjects will be treated for each dose to be tested in Part A1.

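### The ±3-day dosing window lets dose 2 be given on Days 26 to 28 in Parts A and B, before the 28-day DLT period ends

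*Combined protocol and SAP*

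**What the plan says.** Section 7.1 sets the dosing window for IV BMS-986258: "For Q4W dosing cycles, participants may be dosed within a ± 3 -day window". The nivolumab paragraph repeats it: "There will be no dose escalations or reductions of nivolumab allowed. For Q4W dosing cycles, participants may be dosed within a ± 3 -day window". Neither paragraph makes an exception for the second dose.

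The monotherapy escalation in Section 5.1.3.1 uses "planned dose levels of 8, 24, 72, 200, 480, 800, 1200, 1600, and 2400 mg Q4W twice per cycle", with 8-week cycles; Part B is also dosed twice per cycle. Tables 9.5-2 (Part A) and 9.5-4 (Part B) show a predose sample at Cycle 1 Day 29, so that is the nominal day of dose 2.

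Section 7.1.1 defines the observation period: "The DLT period will start on the first day of Cycle 1 and end at Day 28 (therefore, 4 weeks) in Parts A and B". A participant is DLT-evaluable after one dose (of BMS-986258 in Part A, of both drugs in Part B) and completion of that period. The definition does not address a second dose given inside it.

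Section 10.1.1 describes what the dose-escalation models use: "While the BLRM/BLRM-copula will use DLT information from the DLT period only".

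**The concern.** A scheduling tolerance written for every Q4W visit also applies to the one dose that falls the day after the DLT period closes. Its early side therefore reaches into that period.

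Two things follow. First, a participant with no event so far can be redosed before the first-in-human safety observation is finished. The bar on retreatment after a DLT cannot then protect that participant from a first-dose toxicity that emerges in the last days of the period. Second, an event after an early dose 2 but before the end of Day 28 enters the DLT count used by the BLRM or BLRM-copula. For participants redosed on Day 29 or later, the same count reflects a single dose. Section 3.3.6 itself requires close monitoring after each of the first two doses, because reactions may follow the first administration or repeat dosing. A reaction on the day of dose 2 would fall inside the DLT period if that dose were given on Day 28, and outside it if given on Day 29.

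Section 5.1.3.1 treats approximately 3 participants per Part A dose level and allows a decision from 2 evaluable participants. With so few, the exposure behind each contribution should be the same.

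**Working it through.** This is a day count.

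**Inputs**
- DLT period: Day 1 to Day 28 (Section 7.1.1).
- Dosing interval: 4 weeks, two doses per 8-week cycle (Section 5.1.3.1).
- Nominal second dose: Cycle 1 Day 29 (Tables 9.5-2 and 9.5-4).
- Window: ±3 days for each drug (Section 7.1).

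**The plan's own figures**
- Length of the DLT period: 28 − 1 + 1 = 28 days = 4 weeks, as stated.
- Nominal second dose: Day 1 + 28 = Day 29, as in the PK tables.

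**Permitted days for dose 2**
- Earliest: 29 − 3 = Day 26.
- Latest: 29 + 3 = Day 32.

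**Overlap with the DLT period**, for dose 2 on Day *d*:
- First-dose-only days = min(*d* − 1, 28).
- DLT-period days on or after dose 2 = max(0, 28 − *d* + 1).

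| Day of dose 2 | First-dose-only days | DLT days on or after dose 2 | Share of 28 days |
|---|---|---|---|
| 26 | 25 | 3 | 3/28 = 10.7% |
| 27 | 26 | 2 | 2/28 = 7.1% |
| 28 | 27 | 1 | 1/28 = 3.6% |
| 29 to 32 | 28 | 0 | 0% |

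**With a 0/+3-day window**, dose 2 falls on Days 29 to 32. Every participant then has 28 first-dose-only days, and no DLT-period day follows dose 2.

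**Other rules that might close the gap.** Section 7.4.1 withholds all study drug for "Potential DLTs, until DLT relatedness is defined", and also for any event or laboratory abnormality that the investigator judges to warrant delay. Section 7.1.1 bars retreatment after a DLT. Section 3.3.6 schedules laboratory tests and a targeted examination before dosing. These act once something has appeared. None stops an early second dose in a participant who has shown nothing yet.

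**The case against.** The strongest reply is that nothing in the readable protocol is contradicted. Section 7.1.1 sets the DLT period to guide escalation decisions, not as a gate on each participant's next dose, and no text requires first-dose-only observation. The period still runs its full 28 days. Anyone redosed early would have had safety checks and no current potential DLT. Toxicity beyond the DLT period is considered in dose-level decisions anyway (Sections 5.1.3.1 and 5.1.3.2), and Section 10.1.1 brings the totality of data into the clinical assessment. Section 3.3 reports no DLTs in 25 monotherapy participants at the 12-Sep-2019 cutoff, and none in 4 combination participants during their 28 days. The fix would therefore reach only cohorts still to be dosed. It would also need ethics approval as a protocol change.

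Much of this stands. The effect on the DLT count is small and runs in the cautious direction: an early dose can add events but cannot erase first-dose events, and an added event is still toxicity at the assigned dose level. Early dosing is permitted, not required. The Schedule of Activities is not readable, so a narrower window there cannot be ruled out.

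The reply does not remove the point. The safeguards respond to events that have already appeared, whereas the gap concerns a participant whose observation is unfinished. Clinical judgement may weigh a post-dose-2 event correctly, but the model would still count it as a DLT-period event. The protocol already guards this interval against another confounder: Section 7.7.3.1 asks for Medical Monitor consultation before palliative radiation in participants who have not completed it.

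**Conclusion.** The concern holds. On the readable text, dose 2 may be given up to 3 days before Day 29, leaving as few as 25 of 28 days of first-dose-only observation. The consequences are modest: possible redosing before observation is complete, and unequal exposure within a DLT count taken from small cohorts. No change in the DLT rate is claimed, because neither the use of the early window nor the DLT criteria can be read here.

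The conclusion rests on two assumptions. The ±3-day window is taken to apply to the within-cycle Day 29 dose, which is the natural reading of Q4W dosing twice per cycle. It is also assumed that the Schedule of Activities does not already narrow the window for that visit. If it does, only a cross-reference is needed. The change should be made for any escalation cohorts still to be dosed.

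**What to change.** Add one sentence to Section 7.1, covering both BMS-986258 and nivolumab: in the Part A and Part B dose-escalation cohorts, the Cycle 1 Day 29 dose may be given on Day 29 to Day 32 only (0/+3 days), after the Day 1 to 28 DLT period is complete. Keep ±3 days for all later doses. If the Schedule of Activities already sets this window, refer to it in Section 7.1 instead.

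The cost is slightly less scheduling flexibility at one visit. No extra participants, visits or procedures are needed. As a protocol change it needs the usual ethics approval, so it can be carried in the next amendment.

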7.1.1 Dose-Limiting Toxicities

For the purpose of guiding decisions regarding dose escalation in Parts A and B, DLTs will be defined based on the incidence, intensity, and duration of AEs for which no clear alternative cause is identified. The DLT period will start on the first day of Cycle 1 and end at Day 28 (therefore, 4 weeks) in Parts A and B. The severity of AEs will be graded according to NCI CTCAE v4.03.

[figure not shown]
Protocol Amendment No.: 07

For the purpose of participant management, DLTs that occur at any time, whether during dose escalation (Part A or B), SC dose(s) (Part A1), or cohort expansion (Part C), will result in study drug being held pending evaluation of the event being related to study drug, in accordance with Section 7.4.

A participant is considered DLT evaluable if receiving 1 dose of BMS-986258 in Part A or 1 dose of BMS-986258 and nivolumab 480 mg in Part B and completing the DLT observation period. Participants who withdraw from the study during the 4-week DLT evaluation period for reasons other than a DLT may be replaced with a new participant at the same dose level. The incidence of DLT(s) during the 4-week DLT evaluation period will be used in dose escalation decisions and to define the MTD/RP2D in monotherapy and in combination with nivolumab. AEs occurring after the 4-week DLT period will be considered for the purposes of defining the RP2D upon agreement between the Sponsor and Investigators. Participants experiencing a DLT will not be retreated with study drug and will enter the safety follow-up period of the study.

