4 OBJECTIVES AND ENDPOINTS

Objectives	Endpoints
Primary	
To assess the safety, tolerability, and to determine MTD or MAAD and RP2D of BMS-986258 administered as monotherapy and in combination with nivolumab in participants with select advanced solid tumors.	Incidence of AEs, SAEs, AEs meeting protocoldefined DLT criteria, AEs leading to discontinuation, and death.
Secondary	
To assess the preliminary anti-tumor activity of BMS-986258 as monotherapy and in combination with nivolumab in advanced solid tumors.	 ORR, mDOR, and PFS rate at 6, 9, and 12 months. Summary measures of PK parameters of
2. To explore the PK of BMS-986258 when administered IV as monotherapy and in combination with nivolumab.	BMS-986258 after monotherapy and combination treatment.
3. To characterize the immunogenicity of BMS-986258 as monotherapy and in combination with nivolumab.	3. Incidence of ADA to BMS-986258.

Abbreviations: ADA, anti-drug antibody; AE, adverse event; BMS, Bristol-Myers Squibb;
; DLT, dose-limiting toxicity;
; IV, intravenous; MAAD, maximum administered dose; mDOR, median duration of response; MTD, maximum tolerated dose;
; ORR, overall response rate; OS,

overall survival; PFS, progression-free survival; PK, pharmacokinetics; ; RP2D, recommended Phase 2 dose; SAE, serious adverse event; ; SC, subcutaneous;

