10.2 Populations for Analyses

For purposes of analysis, the following populations are defined in Table 10.2-1 below:

Table 10.2-1: Population for Analyses

Population	Description
Enrolled	All participants who sign informed consent and are registered into the IRT.
Treated	All participants who take at least 1 dose of study treatment.
Response-evaluable	All treated participants with measurable disease at baseline and one of the following: (a) at least 1 post-baseline tumor assessment, (b) clinical progression, (c) death.
Pharmacokinetic	All treated participants who have concentration-time data.
Immunogenicity	All treated participants who have baseline and at least 1 post baseline pre-infusion immunogenicity assessment.

Abbreviations: IRT, Interactive Response Technology.

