10.3 Statistical Analyses

The Statistical Analysis Plan will be developed and finalized before database lock and will describe the selection of participants to be included in the analyses. Below is a summary of planned

Protocol Amendment No.: 07

statistical analyses. Results will be presented by study part; data for participants who cross over from the SC cohort (A1) to IV monotherapy or combination treatment will be tabulated separately.

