10.3.2 Safety Analyses

All safety analyses will be performed on the treated population.

Endpoint	Statistical Analysis Methods
Incidence of AEs, SAEs, AEs meeting protocol defined DLT criteria, AEs leading to discontinuation, and death	DLT rate by dose level, frequency distribution of treated participants with AE using the worst CTC grade. Participants will only be counted (1) once at the PT level, (2) once at the system organ class level, and (3) once in the 'total participant' row at their worst CTC grade, regardless of system organ class or PT.
Laboratory abnormalities Laboratory values will be graded according to CTCAE v4.03.	Laboratory shift table using the worst CTC grade on treatment per participant

[figure not shown]
Abbreviations: AE, adverse event; CTC, common terminology criteria; CTCAE, common terminology criteria for adverse events; DLTs, dose-limiting toxicities; PT, preferred term; SAE, serious adverse event.

Protocol Amendment No.: 07

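### The DLT-evaluable definition does not cover a DLT that ends observation before Day 28, and the reported DLT rate uses all treated participants with no stated window

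*Combined protocol and SAP*

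**What the plan says.** **Definition.** Section 7.1.1 sets the DLT window as Cycle 1 Day 1 to Day 28 in Parts A and B. To be DLT-evaluable, a participant needs one dose of BMS-986258 (Part A) or "1 dose of BMS-986258 and nivolumab 480 mg in Part B and completing the DLT observation period". Completing the window is required in both parts. The same paragraph allows replacement of participants who withdraw in the window for a reason other than a DLT. It also bases escalation and the MTD/RP2D on DLT incidence within the four weeks.

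**Reporting.** Section 4 includes in the primary endpoint "AEs meeting protocoldefined DLT criteria, AEs leading to discontinuation, and death". Section 10.3.2 says "All safety analyses will be performed on the treated population" and gives the method as "DLT rate by dose level, frequency distribution of treated participants with AE using the worst CTC grade". Table 10.2-1 defines treated as "All participants who take at least 1 dose of study treatment". Its five populations do not include a DLT-evaluable set. Section 10.3 announces a Statistical Analysis Plan that "will describe the selection of participants to be included in the analyses".

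**Early leavers.** Section 5.1.3 plans for "unforeseen discontinuations (such as disease progression) before the 4-week DLT period (28 days) is completed", and for that reason "an extra participant may be enrolled in each dose escalation cohort".

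**The concern.** There are two separate gaps.

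First, a usual DLT-evaluable definition has two routes in: having a DLT in the window, or completing the window without one. Section 7.1.1 has only the second. A participant who dies of a DLT before Day 28 is as informative as anyone in the cohort, yet the literal wording makes that person non-evaluable. Section 10.1.1 uses this unit for the minimum number at the MTD and the maximum per dose level.

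Second, the DLT rate is a component of the primary endpoint, and section 10.3.2 puts it on everyone dosed. A participant who leaves in the window without a DLT has not been observed for the full 28 days but still counts in the denominator as if DLT-free. Two dose levels with the same DLTs among fully observed participants could therefore show different rates only because one had an early leaver. Section 10.3.2 also does not say whether its numerator stops at Day 28.

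**Working it through.** The visible text gives no DLT rate, target interval or evaluable sample size to reproduce. The check is therefore a reading of the definitions plus simple proportions. The cohort outcomes are illustrations, not trial data.

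**Step 1: who counts under each rule**

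| Participant (Parts A and B, dosed) | 7.1.1 read literally | Evident intent | 10.3.2 denominator |
|---|---|---|---|
| DLT, followed to Day 28 | evaluable | evaluable | counted |
| DLT, observation ends before Day 28 | **not evaluable** | evaluable | counted |
| No DLT, completes Day 28 | evaluable | evaluable | counted |
| No DLT, leaves before Day 28 | not evaluable | not evaluable, may be replaced | **counted** |

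Row 2 is the definition gap. The intent follows from the replacement sentence in 7.1.1: only withdrawals for other reasons are replaceable, so a DLT withdrawal is meant to stay in. Row 4 is the reporting gap. The two do not overlap: a participant in row 2 is in the treated population, so the definition gap does not change the 10.3.2 rate.

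**Step 2: size of the dilution.** Let d be DLTs, n the participants with a DLT in the window or a completed window, and e the early leavers without a DLT. The rate on those observed is d/n, the rate on treated is d/(n+e), and the relative loss is e/(n+e). Section 5.1.3 starts cohorts with 3 participants, or 4 with the spare.

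| d | n | e | d/n | d/(n+e) | Relative loss |
|---|---|---|---|---|---|
| 1 | 3 | 1 | 33.3% | 1/4 = 25.0% | 1/4 = 25% |
| 1 | 6 | 1 | 16.7% | 1/7 = 14.3% | 1/7 = 14% |
| 2 | 6 | 1 | 33.3% | 2/7 = 28.6% | 1/7 = 14% |
| 2 | 6 | 2 | 33.3% | 2/8 = 25.0% | 2/8 = 25% |

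If d = 0 both rates are 0%. If e = 0 they are equal.

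**Step 3: the window.** With 6 treated, one DLT by Day 28 and one event meeting DLT criteria later, the rate is 1/6 = 16.7% with a 28-day numerator and 2/6 = 33.3% without a window. An unstated window can therefore move the rate in the opposite direction.

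**Step 4: replacement.** For a participant who leaves the study in the window because of a treatment-related AE that is not a DLT, 7.1.1 permits replacement and 7.2 rules it out. Take 3 treated, with one DLT and one such leaver. Without replacement, the rate is 1/2 = 50.0% on those observed and 1/3 = 33.3% on treated. With a replacement who completes without a DLT, it is 1/3 = 33.3% and 1/4 = 25.0%.

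**Step 5: data so far.** Section 3.3 reports no DLTs in 25 monotherapy participants up to 1200 mg and none in 4 combination participants at 480 mg. On those data the 28-day rate is 0% on either denominator.

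**The case against.** The best defence is that this is wording, that the intent is plain, and that nothing has gone wrong yet. Much of that stands.

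- **Few participants fall in the definition gap.** Stopping drug does not end observation. Section 7.1.1 sends a participant with a DLT into safety follow-up, 5.1.4.1 requires the follow-up visits unless consent is withdrawn, and 8.2 keeps those who stop treatment in the study. Only death, full withdrawal of consent or loss before Day 28 is left.
- **The treated population is a legitimate safety set.** This stands for every other safety table. It does not answer the point about a 28-day risk among people not observed for 28 days.
- **The SAP can settle it.** Section 10.3 leaves selection of participants to the SAP, which could add a rate on an evaluable subset. A reader might infer from the blanket sentence in 10.3.2 that the SAP is barred from doing so, but the documents do not support that. What remains is that the stated default is the treated population and no DLT-evaluable set is listed.
- **Days 1-28 is the natural window.** This also stands. The any-time wording in 7.1.1 is for participant management, so reading the dose-level rate as covering the whole treatment period would be strained. The gap is only that 10.3.2 does not state the window, while 5.1.3.3 applies DLT criteria at any time in Part C.
- **The sections can be read together.** A reader might see a contradiction where 5.1.3.1 and 5.1.3.2 mention a potential DLT in a third evaluable participant who is still under observation. That is loose use of the term, since such a participant may still complete the window. The replacement rules are also compatible if 7.2 is taken as limiting the permission in 7.1.1.

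**Conclusion.** Both gaps are in the current text and should be fixed.

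The definition gap is narrow. A reader might infer that an early fatal DLT would be dropped from the Bayesian model or from an escalation decision. The documents do not support that. Section 7.1.1 uses DLT incidence in the window without limiting it to evaluable participants, 3.3.5 draws on all previously dosed participants, and 10.1.1 gives the model the DLT information from the DLT period. The model's data set is not visible. The gap concerns how evaluable participants are counted, and no changed dose decision is shown. The Part A decision trigger in 5.1.3.1 carries its own completion wording, which a new definition alone would not change.

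The reporting gap has more effect. If the visible rule is followed, early leavers without a DLT lower the reported rate by 14% to 25% in relative terms over the four cases in the dilution table. This assumes at least one DLT and at least one such leaver at the dose level, and it is zero otherwise. It affects the reported primary safety table, not the BLRM or the MTD/RP2D decision. Confidence is high on the missing route in 7.1.1 and on the denominator and unstated window in 10.3.2. It rests on the visible text, as the separate SAP was not available.

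**What to change.** 1. In 7.1.1, define DLT-evaluable (Parts A and B) as having received the required Cycle 1 Day 1 dose or doses and either having had a DLT in Days 1-28 or having completed the window without one.
2. Add this set to Table 10.2-1.
3. In 10.3.2, report the Day 1-28 DLT rate by dose level on this set. Keep the treated population for all other safety tables, and show events meeting DLT criteria after Day 28 separately.
4. Align the use of evaluable and completed in 5.1.3.1 and 5.1.3.2 with the revised definition.
5. Reconcile the replacement wording in 7.1.1 and 7.2 for a treatment-related AE that is not a DLT.

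The cost is protocol and SAP wording and one extra table row, with no new data collection. The reported DLT rate may look slightly less favourable at dose levels with early leavers.
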